## 6.2 Adequacy of protection against risks.

General procedures to protect against risks: Before initiating any research activity, each subject must give informed consent that will detail the risks of study participation. Eligibility will be determined by the medical and psychiatric history, drug use history, and the physical examination done prior to beginning this research protocol. Subjects will be provided a number to call to reach an on-call psychiatrist (24 hours/day) should unpleasant effects occur after subjects have left the testing facility. We ask subjects to contact us on the day following tests on a routine basis and if we are not contacted, we will call the subjects to monitor their status.

- 1) Protection against adverse events from ALLO: To minimize risks associated with ALLO, subjects will be closely monitored throughout the laboratory session. The targeted plasma level of ALLO (100 nM) used in this study has been used safely in studies with healthy human subjects. The dose is higher than circulating levels of ALLO in men and women but comparable to circulating levels recorded in women during pregnancy.
- 2) a) The administration of alcohol to human subjects proposed in this study is in compliance with NIAAA guidelines for alcohol administration. Subjects are carefully screened so only those who have experience with the dose of alcohol will be enrolled and those that are treatment seeking will be excluded. The clamping procedure is safe and has been used safely with blood alcohol levels up to 0.15 g/dL. The ethanol dose employed in this study is equivalent to doses used in previous studies in healthy human subjects and falls within ranges that alcohol dependent individuals self-administer. No fetus will be exposed to alcohol: pregnancy tests will be administered on the day of testing to every female subject with positive results excluding participation. Women who are breastfeeding will not be included in this study.  
b) We have instituted several levels of medical monitoring including: i) the testing facility is covered at all times by the VA Connecticut Healthcare System (VACHS) medical emergency ("Medical Code") team, ii) the nurses in the testing facility are all certified in advanced cardiac life support, iii) there is continuous medical and nursing presence throughout the test day, iv) subjects will be administered alcohol only if the systolic blood pressure is <150 mmHg and heart rate is <90 beats/minute. Subjects will be terminated from the study if the blood pressure at any time is >170/110 mm Hg or if the heart rate is >130 beats/min.  
c) At the end of each test day, the research staff will review the experiences of the day with the research subject. Subjects will not be released from the Laboratory until the BrAc is less than or equal to 0.02 g/dL (0.02 g/dL is below the threshold of BrAc associated with any impairment in locomotor coordination or judgment in humans) and research personnel have documented that participants exhibit an alert and oriented demeanor.  
d) At the end of the test session, we will provide participants with a brief motivational interview based on the principles of Miller's Motivational Enhancement Therapy. This interview will be conducted by a member of our research group, an M.D. or Ph.D. previously trained in motivational interviewing. During this 30minute interview, participants' drinking and smoking behavior (for the subgroup of smokers), and experience of alcohol and smoking-related problems will be reviewed. Participants will be presented with normative drinking information, as well as guidelines for non-hazardous alcohol consumption. If interested,

participants will be given treatment referrals to address their drinking and smoking behavior (for smokers). It has been found that similar brief advice is associated with decreases in alcohol drinking behavior and increased motivation to quit drinking.

e) All participants will be contacted approximately 1 business day and 1 month after the end of their participation to ensure no residual effects from ALLO or alcohol administrations.

- 3) Stress induction: Similarly to above we have instituted several levels of medical monitoring including: i) the testing facility is covered at all times by the VA Connecticut Healthcare System (VACHS) medical emergency (“Medical Code”) team, ii) the nurses in the testing facility are all certified in advanced cardiac life support and one of the four nurses have extensive medical ICU experience, iii) there is continuous medical and nursing presence throughout the test day, iv) at the end of the test day, the research staff will review the experiences of the day with the research subject. The subject will not be released from the unit unless his/her anxiety, psychological discomfort, and alcohol craving have returned to baseline levels. At the end of the lab session, we will provide participants with a brief motivational interview based on the principles of Miller’s Motivational Enhancement Therapy (details outlined above).
- 4) Blood drawing: The medical staff who perform blood drawing are trained individuals and follow Standard Precautions.
- 5) Confidentiality will be protected by having records identified by code number only with the master list including names kept in a sealed envelope in a locked file in the Principal Investigator's office and by the pharmacy, or on the VA secure server. Subjects will be given telephone numbers to call in case of emergency, 24 hours a day.

Stopping rules: Subjects will be terminated from the study if the blood pressure at any time is  $>170/110$  mm Hg or if the heart rate is  $>130$  beats/min. Subjects will remain in the laboratory until the breathalyzer reaches  $\leq 0.02$  g/dL. These procedures have been developed as part of our routine procedures for IV alcohol administration. Blood pressure and heart rate will be monitored frequently during the lab session. If blood pressure and/or heart rate exceeds these parameters, the infusion will be terminated. If blood pressure does not improve after the infusion is terminated, an MD will evaluate the subject and make a determination regarding rescue medications. If symptoms do not improve the patient will be escorted to the ER if deemed necessary.

6.3 Potential benefits of the proposed research to the subjects and others. Study participation may help the participants to seek help for their alcohol use. At the end of the study, if interested, participants will be referred to clinical programs.

6.4 Importance of the knowledge to be gained. This proposed study may help to develop new and more effective treatments for AUD. We believe that the risk/benefit ratio for this study is acceptable, and that the benefits of the proposed studies outweigh the potential risks to subjects.

6.5 Data safety and monitoring plan. The risk associated with participating in this study is moderate, because ALLO administration may be associated with mild side effects and the effects of the stress-induction procedure are expected to normalize quickly. Serious side effects associated with this study are not expected. This project will be monitored by a Data and Safety Monitoring Board (DSMB), because the study involves double-blind administration of ALLO in combination with alcohol in AUD participants. This board is composed of persons not otherwise affiliated with the study who are

experienced in various aspects of the conduct of clinical trials, laboratory studies and treatment of addictive disorders. We propose three investigators located here in Connecticut who are not directly involved in this study – [name]., [name]., and [name]. as the members of the DSMB. The members of the DSMB and all study Investigators will complete Conflict of Interest forms created by Yale's IRB in accordance with NIH guidelines.

We will report recruitment, follow-up, and adverse events to this panel on a quarterly fashion. Prior to study initiation, critical parameters for collection of side effects and for study discontinuation will be recommended to the DSMB who may use these or other measures to monitor safety of the ongoing study. The DSMB will be available to convene outside of scheduled meetings, if necessary, due to concerns regarding a particular subject or due to any troublesome developments in subjects' experiences during the study. The DSMB will make appropriate recommendations for changes in the study protocol, if needed.

This monitoring will be consistent with NIH policy regarding the protection of human subjects in research, and FDA guidance on statistical practices for clinical trials (ICH E9) and good clinical practices (ICH E6). In general, the data to be reviewed will include screening data, baseline data, laboratory data, and safety data.

The Principal Investigator will conduct a review of all adverse events and determine the attribution and grade of severity of the adverse event by using the following scales:

**Attribution of Risk Categories:**

Definite: Adverse event(s) will clearly be related to investigational agent(s) or other intervention

Probable: Adverse event(s) will likely be related to investigational agent(s)

Possible: Adverse event(s) may be related to investigational agent(s)

Unlikely: Adverse event(s) will doubtfully be related to investigational agent(s)

Unrelated: Adverse event(s) will clearly not be related to the investigational agents(s)

**Grades of Risk:**

0: No adverse event or within normal limits

1: Mild adverse event

2: Moderate adverse event

3: Severe adverse event resulting in hospitalization or prolongation of existing hospitalization, a persistent or significant disability/incapacity, or a congenital anomaly/birth defect

4: Life-threatening or disabling adverse event

5: Fatal adverse event

Serious adverse events (SAEs) include any untoward medical occurrence that results in death or the immediate risk of death, hospitalization or the prolonging of an existing hospitalization, persistent or significant disability/incapacity or a congenital anomaly/birth defect. Subjects will be terminated from participation if the investigator feels that subjects' health or well-being may be threatened by continuation in the study. Serious unanticipated and anticipated adverse events will be reported within 48 hours to the VA Hospital and Yale IRBs, and NIAAA. We will directly report to the FDA, whenever their magnitude or frequency exceeds expectations.

6.6 Clinicaltrials.gov requirements. This study will be registered at the clinicaltrials.gov website.

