
**Please note:** Since this is the first study that combines ALLO with alcohol we propose to run at least one subject under open-label condition at a targeted plasma of 50nM (To target 50 nM: 95.5 mcg/kg/hr x 1 hour loading dose, then 28.7 mcg/kg/hr maintenance infusion, and at least one subject under open-label condition at a targeted plasma of 100Nm (To target 100 nM: 191 mcg/kg/hr x 1 hour loading dose, then 57.4 mcg/kg/hr maintenance infusion).

**Justification for use of ALLO and dose:** ALLO was chosen because it can be administered directly, and for its robust action on the GABAa receptors; this is believed to be responsible for the anxiolytic, analgesic, antiepileptic and neuroprotective properties of neurosteroids. We considered other neurosteroids, such as PROG. PROG is not of interest in this study because it does not bind directly to GABAa receptors and it has been widely accepted that the non-reproductive actions of PROG are mediated by ALLO. ALLO is currently not widely available in the US, but it has been studied previously in Europe. [name] laboratory has extensive experience with ALLO, and is the only laboratory that holds an IND for the clinical use of ALLO in the US. He will be providing ALLO for this study. [name] will hold the IND (140598) for this study and will reference [name] IND for ALLO (IND111085) and [name] IND for Alcohol (IND121915). However, the sterile injectable vials of ALLO will be compounded at an FDA registered 503B outsourcing facility. His lab is now investigating the efficacy of ALLO in TBI (NCT01673828) and Alzheimer's disease (NCT02221622). We selected the dose in consultation with [name], and is designed to maximize behavioral effects while limiting side effects such as sedation, alcohol-like intoxication, mild nausea, and flushing.

**Justification for study design:** 1. We decided to use continuous infusion of ALLO because bolus (i.e., rapid IV push) infusion leads to rapid and dramatic increases in ALLO followed by a precipitous

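### Grade 3 is defined by seriousness outcomes, so a severe but non-serious reaction can be graded no higher than moderate; separately, the DSMB is not on the 48-hour SAE list

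*Combined protocol and SAP*

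**What the plan says.** Section 6.5 (Data safety and monitoring plan) has the Principal Investigator assign an attribution and a severity grade to each adverse event. Under Grades of Risk, grades 1 and 2 are bare labels; the second reads only "2: Moderate adverse event". The next two entries are "3: Severe adverse event resulting in hospitalization or prolongation of existing hospitalization", which goes on to add disability and birth defect, and "4: Life-threatening or disabling adverse event". Grade 5 is a fatal event.

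Below the scale, SAEs are defined by outcome: death, immediate risk of death, hospitalisation or its prolongation, disability, or birth defect. Serious events, expected or not, "will be reported within 48 hours to the VA Hospital and Yale IRBs, and NIAAA". The FDA is told when their size or frequency is greater than expected, with no time limit given.

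On the DSMB, section 6.5 says that it exists because ALLO is given double-blind together with alcohol. It states: "We will report recruitment, follow-up, and adverse events to this panel on a quarterly fashion". The board may also meet between scheduled dates over a particular participant or a worrying development. Parameters for side-effect collection and for discontinuing the study are to be recommended to it before the start; the document does not list them.

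The stopping rules in section 6.2 describe reactions short of admission. If blood pressure exceeds 170/110 mm Hg or heart rate exceeds 130 beats/min, the infusion is ended, a physician may evaluate the participant, and "If symptoms do not improve the patient will be escorted to the ER if deemed necessary".

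**The concern.** Severity (how intense an event is) and seriousness (what it led to) are different attributes. The scale uses the second to define its only grade named severe. Short, monitored, single-day infusions can produce reactions that are intense but reversible, and for those the scale cannot separate moderate from severe. In a first study of this combination, that distinction is a main reason for grading events at all.

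The second matter is independent of the first. The board set up to oversee the combination is not among those told of an SAE within 48 hours. Further participants could complete their single test day before the board hears of it.

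**Working it through.** No sample size, power or event rate enters here. The check sets the definitions and the reporting rules of section 6.5 side by side.

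**Step 1. Lowest grade that each SAE criterion allows.**

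- Death: grade 5.
- Immediate risk of death: grade 4.
- Hospitalisation or its prolongation: grade 3.
- Disability or incapacity: grade 3 (also fits grade 4).
- Birth defect: grade 3.

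So 0 of the 5 SAE criteria can fall to grade 2.

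**Step 2. An intense event with none of these outcomes.** Take marked sedation managed in the laboratory, or a blood pressure or heart rate over the section 6.2 limits, with the infusion ended, an ER evaluation and no admission. It is not life-threatening and leaves no disability.

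- Grade 3 needs one of three outcomes; none is present.
- Grade 4 needs a life-threatening or disabling event; it is neither.
- The highest grade left is 2.
- It meets none of the listed SAE criteria, and the list has no item for other medically important events. No 48-hour report is therefore due to anyone.

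**Step 3. Overlap.** Disability is one of the grade 3 outcomes, and a disabling event is grade 4. The same event fits both, with no rule for choosing.

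**Step 4. Who is told, and when.**

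- SAE to the IRBs and NIAAA: within 48 hours, or 2 days.
- SAE to the DSMB: the only fixed timing is the quarterly report. One quarter is 365 / 4 = about 91 days, so the longest wait is about 91 days, or 91 - 2 = 89 days after the other recipients' deadline.
- Ad hoc DSMB meeting: possible on general grounds, but with no defined trigger, no deadline and no person charged with alerting the board.

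**Step 5. Whether the two gaps are linked.** They are not. The 48-hour rule follows the SAE definition, and no reporting rule refers to grade. An SAE receives grade 3 or higher but may reach the board late. A severe non-serious event is graded too low, but under the present rules it would have no expedited route at any grade.

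**The case against.** The strongest reply is that participants are protected in other ways. Medical and nursing staff are present throughout, the investigator reviews every event and can end participation, and the board can meet at any time. The parameters to be recommended to the board before the start might also include alert triggers. All of this stands, and it is why the 91 days is a ceiling and not an expected delay. It does not repair the scale, though: bedside monitoring does not change the grade recorded. Nor does it put the DSMB on the 48-hour list, and triggers that may be agreed later are not yet a rule.

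Three stronger readings are tempting, and the documents do not support them.

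- A reader might infer that serious reactions can be coded moderate. Step 1 shows that none of the SAE criteria allows it.
- A reader might infer that under-grading delays reports. Step 5 shows that reporting does not run through the grade.
- A reader might infer that the trial's tolerability conclusion will be biased. No endpoint or analysis in the Data Analysis section uses adverse-event grade, and sedation is scored directly on the visual analogue scale and the BAES. The protocol expects mainly mild sedation, so it gives no ground for saying that severe reactions will be common or systematically under-graded.

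**Conclusion.** The point holds as two separate and modest defects. First, the scale has no place for a severe reaction without a seriousness outcome; followed as written, it caps such an event at grade 2, and it puts disability in two grades. Second, the DSMB is missing from the 48-hour SAE recipients, so an SAE could reach it up to about 91 days later without any breach of the plan, unless someone uses the ad hoc route.

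This rests on two assumptions: that an ER visit without admission is not hospitalisation, which the document does not settle, and that no separate DSMB document already sets faster notice. The number of events affected cannot be estimated, because the plan gives neither an expected rate of severe non-serious reactions nor the number of sessions per quarter. The matter concerns the quality of the safety record and of oversight; the efficacy analyses are unaffected.

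**What to change.** 1. In Grades of Risk, define grades 1 to 3 by intensity alone, with short descriptions set by the investigators. Put disability in one grade only. Record seriousness as a separate yes/no item, using the SAE definition already in section 6.5. Do not make an ended infusion or an ER visit a criterion for severity. Those are actions taken, and using them would again mix severity with something else; a symptom-free reading just over a limit would become severe.

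2. Add the DSMB to the 48-hour SAE recipients. On the same clock, notify it of any event of grade 3 or higher and of any infusion stopped for safety, and name the role responsible. This also gives the ad hoc meeting a stated trigger.

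The cost is a few sentences in section 6.5 and one change to the adverse-event form. More events will be labelled severe, and an existing board will receive a few more notices. No dose, schedule or stopping limit changes.

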**7. Payment:**

Participants will be paid \$30 for the screening session, \$30 for the script development session, \$150 for attending the test session, and \$0 for the 1 month follow-up. Thus, the total amount that could be earned during the study is \$210. This payment is for the time and effort associated with study assessments and procedures. This payment will be given in the form of cash. Participants will not be paid if a test day is cancelled because they test positive for alcohol or illicit drugs in their system. If a

patient participates in a virtual screening and is not eligible to come for the in-person visits they can choose to come in to pick up their cash payment or be mailed a gift card or check. If they choose to receive payment by gift card or check they may need to complete a tax form.

We will provide participants with 2 meals during the lab visit (breakfast and lunch).

